7.0 TREATMENT MODIFICATIONS

Propranolol can be dose reduced if the patient's heart rate is less than 60 or systolic BP is less than 110 or diastolic less than 50 and showing symptoms at two different timepoints 24 hours apart. Also if the patient has side effects from the beta-blocker a dose reduction can be performed as outlined in Table E. All dose reductions will be made in the clinic. The maximum dose for propranolol should be 40mg po twice a day. For patients > 65 years old the maximum dose will be 20 mg by mouth twice a day. All dose adjustments will be made in the clinic.

Table E Modifications for Propranolol dosing

	Regimen -1 Level	Regimen -2 Level
Starting Dose 20 mg twice daily	10 mg po bid (50%)	Discontinue
Maximum Dose 40 mg twice daily	30 mg po bid (25%)	20 mg po bid (50%)

7.1 Hypotension.

Patients receiving propranolol should be monitored before each dose with measurement of blood pressure (see Section 5.0 Treatment Plan). If the SBP is less than 110 or the DBP is less than 50 and showing symptoms at two different timepoints 24 hours apart, the patient should be dose modified to regimen level -1 (see Table E). If after this dose modification there is still hypotension, then dose modify to regimen level -2 (see Table E). If patient still encounters hypotension, then discontinue the propranolol.

7.2 Bradycardia.

Patients receiving propranolol should be monitored with a measurement of heart rate. If the heart rate is less than 50 or 50-60 and showing symptoms at two different timepoints 24 hours apart, the patient should be dose modified to regimen level -1 (see Table E). If after this dose modification there is still bradycardia, then dose modify to regimen level -2 (see Table E). If patient still encounters bradycardia, discontinue propranolol.

8.0 STUDY PARAMETERS AND SERIAL OBSERVATIONS

8.1 Observations and Tests

The following observations and tests are to be performed and recorded.

Observations and Tests	Prior to Initial Study Treatment	On Treatment			
		Month 1 (+/- 7 days)	Month 2 (+/- 7 days)	Month 4 (+/- 7 days)	End of Study (+/- 7 days)
History & Physical	1			4	
Blood Pressure	1	8	8	8	8
Heart Rate	1	8	8	8	8
Toxicity Assessment	1	8	4	4	4
CBC/Differential/Platelets	1		4	4	4
Serum Creatinine	1		4	4	4
Bilirubin, SGOT, SGPT, Alkaline Phosphatase	1		4	4	4
Magnesium	1		4	4	4
C-Reactive Protein (CRP)	1		4	4	4
PT/INR, PTT	1		5	5	
Serum Pregnancy test if childbearing potential exists	1				
EKG	1		6	6	
Indirect Calorimetry (MDA Pts. Only)	1		4	4	
Palliative Supportive Care	1		6	6	
QOL Surveys	3		7	7	
Demographic information	3				
Blood draw (TR)	3		7	7	
MRI, PET or PET/CT Scan of Chest/Abd/Pelvis	2		6		
Pill Diary		8	4	4	4
Relaxation Log		8	4	4	4

1. Must be obtained within 14 days prior to initiating propranolol therapy.
2. Must obtain CT, MRI or PET within 6 weeks prior to receiving any propranolol therapy.
3. QOL Surveys (MDASI, HADS, BPI, and FACT-Cx), demographic information and translational blood to be performed prior to initial study treatment
4. Must be obtained within +/- 7 days prior to clinic visit.
5. For patients on prophylactic or therapeutic anticoagulation with warfarin, PT/INR should be monitored before.
6. Only if clinically warranted.
7. Biobehavioral measures and QOL Surveys (MDASI, HADS, BPI, and FACT-Cx) are to be administered after completion of months 2 & 4 on trial and blood is to be drawn at clinic visit for translational purposes.

8. Blood Pressure and Heart Rate will be checked prior to starting propranolol in the clinic by research nurse/clinic nurse. At 48-72 hours after starting treatment, blood pressure monitoring needs to be done in the clinic by research nurse/clinic nurse but if patient unable to return to clinic, research personnel will contact patient for blood pressure readings. After that time, patient should continue to monitor blood pressure daily with their personal blood pressure machine, at their local pharmacy, or in the clinic. If personally monitoring their blood pressure, the patient should contact the research nurse if the SBP is less than 110, the DBP is less than 50 or heart rate 50-60 and showing symptoms at two different timepoints 24 hours apart.

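### Footnote 8 of Section 8.1 asks for blood pressure only between visits, although its own heart-rate call trigger and the Section 7.2 bradycardia rule need pulse readings there

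*Combined protocol and SAP*

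**What the plan says.** Footnote 8 to the table in Section 8.1 governs both the Blood Pressure and the Heart Rate rows at Months 1, 2, 4 and End of Study. It contains five instructions:

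- Before the first dose: "Blood Pressure and Heart Rate will be checked prior to starting propranolol in the clinic".
- After the first doses: "At 48-72 hours after starting treatment, blood pressure monitoring needs to be done in the clinic by research nurse/clinic nurse".
- If the patient cannot come back for that check: "research personnel will contact patient for blood pressure readings".
- From then on: "patient should continue to monitor blood pressure daily with their personal blood pressure machine", with a local pharmacy or the clinic as alternatives.
- When to call: "If personally monitoring their blood pressure, the patient should contact the research nurse if the SBP is less than 110", or for a low diastolic pressure, or for "heart rate 50-60 and showing symptoms at two different timepoints 24 hours apart".

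Section 7.2 reduces the dose for a heart rate below 50, or of 50-60 with symptoms, and refers to two timepoints 24 hours apart. On measurement it says: "Patients receiving propranolol should be monitored with a measurement of heart rate". It does not say how often, where or by whom. Section 7.1, by contrast, asks for blood pressure before every dose. On-treatment EKG carries footnote 6: "Only if clinically warranted".

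**The concern.** The call trigger and the bradycardia rule both act on heart rate, but after the first dose nobody is told to measure it until the Month 1 visit. A nurse or patient who follows footnote 8 literally takes blood pressure at 48-72 hours and daily afterwards, and has no pulse to compare with the 50-60 trigger.

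The early period is where this matters most. Section 4.1.8 lists sinus bradycardia first among the side effects and says that side effects tend to appear when therapy starts. Section 5.1 raises the dose at the start of the second month if there has been no hypotension or bradycardia. A visit pulse is scheduled around that decision, but there would be no pulse record from the preceding weeks to support it.

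**Working it through.** **Which vital sign each part of footnote 8 names**

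| Instruction | Blood pressure | Heart rate |
|---|---|---|
| Before first dose | yes | yes |
| 48-72 hour clinic check | yes | no |
| Remote contact instead of that check | yes | no |
| Daily self-check | yes | no |
| Patient call trigger | yes | yes |

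Of the three on-treatment measurement instructions, 3 of 3 name blood pressure and 0 of 3 name heart rate. The trigger that depends on them uses both.

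**Where else a pulse could come from**

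- The Heart Rate row gives a pulse at Months 1, 2, 4 and End of Study. These visits are weeks apart, so they cannot by themselves supply two readings 24 hours apart.
- Section 7.2 requires a heart-rate measurement but sets no schedule.
- On-treatment EKG is done only on clinical indication.
- Section 6.1 lists blood pressure among the safety evaluations and does not name heart rate.

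**Length of the gap**

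Assumptions: a month is 28 to 30 days; visit windows are ±7 days, as in the table; the 48-72 hour check falls on day 2 to 3.

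- First dose to first scheduled on-treatment pulse (Month 1): 28 − 7 = 21 days to 30 + 7 = 37 days, about 3 to 5 weeks.
- 48-72 hour check to Month 1: 21 − 3 = 18 days to 37 − 2 = 35 days.
- Month 4 visit: 4 × 28 − 7 = day 105 to 4 × 30 + 7 = day 127.
- Daily blood-pressure readings from the 48-72 hour check to Month 4: 105 − 3 = 102 to 127 − 2 = 125.
- Scheduled on-treatment pulse readings over the same time: 3 (Months 1, 2 and 4). The count is 4 if Section 15.0, which asks for required parameters before each cycle, is combined with the one-month cycle in Section 5.3 to imply a Month 3 reading. The table has no Month 3 column.
- Month 2 to Month 4, after the planned dose increase: (4 × 28 − 7) − (2 × 28 + 7) = 105 − 63 = 42 days to (4 × 30 + 7) − (2 × 30 − 7) = 127 − 53 = 74 days with no pulse in the table.

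**Call trigger against the dose rule**

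The trigger covers a heart rate of 50-60 with symptoms. Section 7.2 also acts below 50. A patient who does see a pulse below 50 is therefore not told to call, although Section 7.2 treats that range as a reason to reduce the dose.

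**The case against.** The best reply is that pulse was plainly intended. The Heart Rate row cites footnote 8, the footnote opens with both signs and ends with a heart-rate threshold, Section 7.2 says heart rate should be measured, and the rationale at the end of Section 2.6 commits to watching both blood pressure and pulse closely. On that reading, blood pressure monitoring is shorthand for a vital-sign check. Many home machines may show pulse, and a nurse may take it without being told. A symptom-free pulse of 50-60 lies inside the 50-80 titration target in Section 5.1, and symptoms can themselves prompt a call. One low reading can also prompt a second a day later, so the two-timepoint rule does not strictly need a daily pulse. Finally, the pill diary and side-effect sheets (Appendices M-P) are not reproduced and may already ask for pulse.

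Much of this stands. The intent is very likely as described, and a machine that shows pulse would narrow the gap in practice. But intent is not an instruction. None of these passages tells staff to take a pulse at 48-72 hours, tells the person making the remote contact to ask for one, or tells the patient to note one daily. The documents do not say that home or pharmacy devices report pulse. A second reading 24 hours later still needs a first. And none of these passages covers the symptom-free pulse below 50, for which the trigger gives no instruction to call.

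**Conclusion.** The concern holds. As written, footnote 8 leaves its own heart-rate trigger, and the Section 7.2 rule between visits, without the readings they act on. The first scheduled on-treatment pulse comes 21 to 37 days after the first dose, assuming 28-30 day months and the stated windows.

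The point should be corrected, but its size is limited. Pulse is scheduled at the visits, including around the dose-increase decision. Section 3.2.2 excludes bradycardia below 50 at entry. Section 7.0 caps the dose at 40 mg twice daily, or 20 mg twice daily over age 65. The day counts measure the gap in the schedule; they are not an estimate of bradycardia risk. No effect on any endpoint is claimed. Confidence is medium, because the patient-facing appendices are not available and local practice may already include pulse.

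**What to change.** In footnote 8, add *and heart rate* in three places: the 48-72 hour clinic check, the readings requested at the remote contact, and the daily self-check. Have patients write down pulse with each blood pressure reading and bring the record to the Month 1 visit, where the dose increase is decided.

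These edits alone would not make a patient call for a symptom-free pulse below 50. For that, add heart rate below 50 to the call trigger, in line with Section 7.2, and state that symptoms are not required in that range. Without this addition, the clear gains are a pulse at the 48-72 hour check, a usable 50-60 trigger, and a record to review at Month 1.

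The cost is a few words in one footnote, one column in the patient's daily record if it is not already there, slightly more recording by patients and staff, and a hand-counted pulse where a machine shows none. No extra visit is needed.

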3.0 PATIENT ELIGIBILITY

3.1 Inclusion:

- 3.1.1 Proven recurrent cervical cancer of any histology not eligible for curative radiotherapy or surgery.
- 3.1.2 Failed chemotherapy for first recurrence (excluding chemotherapy with concurrent irradiation) or refractory to first line systemic therapy.
- 3.1.3 Measurable or non-measurable disease
- 3.1.4 Unlimited prior therapies

3.2 Exclusion:

- 3.2.1 Patients whose disease may be cured by surgery or radiotherapy.
- 3.2.2 Contraindication to use of a β -blocker.(uncontrolled DM, COPD-unstable, Bradycardia <50 BPM)
- 3.2.3 Already receiving a β -blocker.
- 3.2.4 Performance status > 3. Must have had treatment for first line recurrence
- 3.2.5 Prior radiation therapy for localized cancer of the breast, head and neck, or skin is permitted provided that it was completed more than 3 years prior to registration, and the patient remains free of recurrent or metastatic disease.
- 3.2.6 With the exception of non-melanoma skin cancer and other specific malignancies as noted above, patients with other invasive malignancies who had (or have) any evidence of the other cancer present within the last five years or whose previous cancer treatment contraindicates this protocol therapy are excluded.

- 3.2.7 Use of systemic glucocorticoids such as Prednisone or Decadron in the last month for greater than one week
- 3.2.8 Inability to accurately answer questions (e.g. dementia, brain metastases) or speak English or Spanish.
- 3.2.9 Cirrhosis of the liver
- 3.2.10 Patients under the age of 18
- 3.2.11 History of comorbid conditions: Addison's disease, autoimmune hepatitis, hepatitis B, hepatitis C, AIDS or HIV, lupus erythematosus, mixed connective tissue disease, rheumatoid arthritis.
- 3.2.12 Hypersensitivity to propranolol, or beta-blockers
- 3.2.13 Uncompensated congestive heart failure
- 3.2.14 Cardiogenic shock
- 3.2.15 Severe sinus bradycardia; heart block, second or third degree or sick sinus syndrome (if no artificial pacemaker present)
- 3.2.16 Severe hyperactive airway disease (chronic obstructive pulmonary disease, asthma)
- 3.2.17 Any patients on Avastin or any other anti-angiogenic drugs.
- 3.2.18 Patients with brittle diabetes mellitus (DM) Brittle diabetes mellitus is a type of diabetes when a person's blood glucose (sugar) level often swings quickly from high to low and from low to high. Also called "unstable diabetes" or "labile diabetes."

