5.0 PROPOSED TREATMENT/STUDY PLAN

5.1 Dosing of Propranolol

A pill diary will be provided that is a monthly calendar on which patients will record the study medication they take each day. Every dose will be documented and if doses are missed, the patient will be asked to note why they missed a dose. Calendars, empty bottles and any unused medication will be collected at each appointment before the next refill is given to the patient.

Propranolol will be provided to the participant free of charge.

A starting dose of propranolol 20 mg is taken by mouth twice a day (40 mg/day). If the patient tolerates the initial dose (no hypotension or bradycardia) the dose will be increased to 40 mg by mouth twice a day at the start of the second month of therapy. This will ideally be titrated up to 40 mg twice a day in order to maintain a heart rate between 50 to 80 bpm without symptoms or hypotension (systolic BP <110 or diastolic BP <50). For patients > 65 years old the dose will stay at 20 mg by mouth twice a day. Dose reduction to 10 mg administered by

mouth twice a day will be allowed for titration for optimization of BP and pulse. All dose adjustments will be made in the clinic.

To insure compliance, patients will fill out pill calendar diaries that will be collected on a monthly basis.

If removed from study, all patients will be weaned off the medication over the following 2 weeks. The dose will be reduced by 50% for 7 days then will be reduced to 25% of the dose for 7 days then discontinue completely. For patients that experience adverse effects during weaning the period of time can be increased as deemed appropriate.

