5.3 Methodology

After a patient is deemed eligible for the study, she will be asked to provide consent to participate. If consent is given, at this time the patient will be given a demographic questionnaire (age, race, marital status, and smoking history) and the Functional Assessment of Chronic Illness Therapy-Cervix (FACT-Cx), Brief Pain Inventory (BPI), MD Anderson Symptom Inventory (MDASI) and Hospital Anxiety and Depression Scale (HADS). Additionally, blood will be drawn from the patient in the clinic prior to the start of the intervention for measurement of baseline IL-6, IL-8, IL-10, circulating HPV DNA, and VEGF levels.

Upon enrollment, all patients will be instructed to listen to MP3-relaxation/guided imagery audio intervention. Patients on protocol will be referred for supportive/palliative care consultation at MDACC or LBJ. At the end of four months, patients will have the option of continuing treatment until intolerability of the treatment, disease progression or death. *Propranolol will be provided to the participants free of charge. Propranolol will be administered at 20 mg twice a day (40 mg/day). This dose will ideally be titrated up to 40 mg twice a day to maintain a heart rate of 50-80 beats per minute without causing hypotension (systolic blood pressure [BP] < 110 mmHg or diastolic BP < 50 mmHg). For patients more than 65 years old, the starting dose will be 20 mg given by mouth twice a day. Dose reduction to 10 mg administered by mouth twice a day will be allowed for titration for optimization of BP and pulse. All dose adjustments will*

be made in the clinic. Blood draws and completed surveys of biobehavioral measures (FACT-Cx, MDASI, HADS, BPI and smoking history) will be collected at baseline and again after the completion of every two cycles (1 month = one cycle) until the 4-month time point. The HADS will be scored and evaluated within 24 hours of completion. The Hospital Anxiety and Depression Scale (HADS) is a 14 item self-administered scale to detect states of depression and anxiety. Respondents answer questions using a scale of 0 (not at all) to 3 (very often). A HADS score of 15 or higher defines clinical depression or anxiety, and those patients will be assessed by their physician, and, if appropriate, referred to psychiatry. Scoring will be done by the research personnel.

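### The call rule for self-monitoring patients (8.1, footnote 8) omits heart rates below 50, a range that 7.2 names for dose reduction, and its out-of-clinic checks name only blood pressure

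*Combined protocol and SAP*

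**What the plan says.** Three parts of the protocol set heart-rate limits for a patient on propranolol.

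- **Call rule (8.1, footnote 8).** A patient monitoring herself is to contact the "research nurse if the SBP is less than 110, the DBP is less than 50 or heart rate 50-60 and showing symptoms", with the symptoms present at two timepoints 24 hours apart.
- **Dose rule (7.2).** The dose goes down to regimen level -1 as follows: "If the heart rate is less than 50 or 50-60 and showing symptoms at two different timepoints 24 hours apart".
- **General dose rule (7.0).** A reduction is allowed when the "heart rate is less than 60 or systolic BP is less than 110", or diastolic pressure is below 50, followed by the same symptom condition.

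Footnote 8 also sets the checks between visits. At 48-72 hours, if the patient cannot come back to clinic, "research personnel will contact patient for blood pressure readings". After that the "patient should continue to monitor blood pressure daily", at home, at a pharmacy or in the clinic. Heart rate is named for the clinic check before the first dose, and the schedule has a heart-rate row that points to footnote 8.

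Two other sections treat 50 bpm as a lower limit. Section 3.2.2 lists "COPD-unstable, Bradycardia <50 BPM" among contraindications at entry. Section 5.1 titrates the dose "in order to maintain a heart rate between 50 to 80 bpm without symptoms or hypotension", and 5.3 repeats the aim: "to maintain a heart rate of 50-80 beats per minute without causing hypotension".

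**The concern.** Sinus bradycardia is a listed side effect of the study drug (4.1.8), and the protocol relies on close observation of blood pressure and pulse to justify using it in this population (2.6). All dose adjustments are made in the clinic, so a low home reading can change the dose only if it reaches staff. The call rule is the stated route for that between visits.

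That rule lists the milder bradycardia range and leaves out the more severe one. Followed literally, it asks a patient with symptoms at 55 bpm to call but does not ask the same of a patient with symptoms at 45 bpm. The sentences setting up the home checks add to the problem, because they do not ask for the heart rate on which the rule depends. What is at stake is timely dose reduction for an individual patient.

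**Working it through.** The plan states no figure on this point, so the check sets the rules side by side.

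**Inputs.** Heart-rate limits come from 7.2 and from footnote 8 of 8.1. Blood pressure is held above the limits (systolic at least 110, diastolic at least 50), so that only heart rate can trigger anything. Symptoms means symptoms at two timepoints 24 hours apart.

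**Two readings of 7.2.** The symptom condition follows both ranges in one sentence. Reading A applies it to both ranges. Section 7.0 gives some support to this, since it puts the same condition after a single cut-off of 60. Reading B applies it only to 50-60.

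| Heart rate, symptoms | Reduce under 7.2, reading A | Reduce under 7.2, reading B | Call under footnote 8 |
|---|---|---|---|
| below 50, with | yes | yes | **no** |
| below 50, without | no | yes | **no** |
| 50-60, with | yes | yes | yes |
| 50-60, without | no | no | no |

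**Result.** The first row is a mismatch on both readings. The second is a mismatch only on reading B. The third and fourth rows agree.

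**Worked case, valid on either reading.** Heart rate 45 with symptoms at two timepoints 24 hours apart, blood pressure 120/70:
- 7.2: 45 is below 50 and symptoms are present, so the dose goes to regimen level -1.
- Footnote 8: 120 is not below 110, 70 is not below 50, and 45 is not within 50-60. No call is prompted.

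**Could 50-60 in footnote 8 be meant to include lower rates?** Section 7.2 lists below 50 and 50-60 as separate ranges, so there 50-60 does not include rates under 50. Nothing in footnote 8 gives the phrase a wider meaning.

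**Out-of-clinic checks.** Both the remote 48-72 hour contact and the daily check name blood pressure; neither names heart rate. A heart-rate reading is implied by the call rule and by the schedule row that points to the footnote, but the instruction is not written.

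**With the corrected trigger** (below 50, or 50-60 with symptoms), a call is prompted in the first three rows. Every state that needs a reduction under reading A or reading B then reaches staff.

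**The case against.** The strongest reply is that this is a drafting slip with little practical effect. Section 7.0 uses one cut-off of 60, and few nurses or patients would conclude that 55 bpm with symptoms needs a call and 45 bpm with symptoms does not. Other safeguards exist: the entry exclusion for bradycardia below 50, heart-rate checks at scheduled visits, adverse-event review at each visit (6.1), monthly drug supply, the general requirement in 7.2 to measure heart rate, and the condition that the dose is raised only without hypotension or bradycardia. Sections 3.2.2, 5.1 and 5.3 are an entry criterion and a titration aim, not on-treatment action limits, so only 7.2 conflicts directly with footnote 8. Most of this stands. It narrows the gap to self-measured readings between visits, but it does not put the missing range into the rule.

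Several stronger inferences are tempting, and the documents do not support them.

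- **That patients are in fact never told to call below 50.** The pill diaries and beta-blocker side-effect sheets (Appendices M to P) are not in the supplied text and may cover it. Only the protocol wording can be faulted.
- **That 7.2 should require a reduction below 50 with or without symptoms.** That would change a dosing rule and could conflict with 7.0. The text does not settle which reading was intended.
- **That low blood pressure would always prompt a call anyway.** The symptom condition at the end of footnote 8 may also cover the blood-pressure limits, so this backstop may be narrower than it looks.
- **That the number of mismatched rows measures risk.** The rows describe wording, not how often patients fall into them.

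**Conclusion.** The point holds as an internal inconsistency in a safety instruction. Footnote 8 omits heart rate below 50, which 7.2 names for dose reduction, and its out-of-clinic checks do not name the measurement that its own call rule requires. The symptomatic case below 50 with normal blood pressure is missed whichever way 7.2 is read. The asymptomatic case is missed only if the symptom condition in 7.2 is confined to 50-60.

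The size is modest. The gap concerns an isolated low rate, measured by the patient herself between visits; readings taken in clinic fall under Section 7 directly. How many patients this would touch cannot be estimated from the documents. A reader might infer that the toxicity criterion or another feasibility conclusion in Section 12 is compromised. Nothing in the documents shows that, and it is not claimed.

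Confidence is high for the wording mismatch. Whether any patient would actually go without an instruction depends on the appendices that were not supplied. The correction is worth making because the rule gives the wrong result when followed literally and the change costs almost nothing.

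**What to change.** 1. In footnote 8 of 8.1, and in any patient instructions that repeat it, make the heart-rate trigger: heart rate less than 50, or 50-60 with symptoms at two timepoints 24 hours apart. As punctuated, any reading below 50 prompts a call. A call is not a dose change, so this does not prejudge how 7.2 is read.
2. Add heart rate next to blood pressure in the 48-72 hour check and in the daily check.
3. Leave the dose-reduction rule in 7.2 unchanged. Whether its symptom condition applies below 50 is for the investigator to clarify, together with 7.0 so that the two sections agree.
4. Check Appendices M to P against the revised footnote.

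The cost is a wording change, one extra value per home reading and possibly a few more calls to the research nurse. No visits or tests are added.

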4.1.7 Drug Interactions: (www.clinicalpharmacology-ip.com)

Adenosine
Anti-arrhythmic drugs (flecainide, propafenone, moricizine, encainide)
Amiodarone
Bretyllium
Calcium-blocking blood pressure drugs such as diltiazem, nifedipine, and verapamil
Certain high blood pressure medications such as reserpine
Cardiac glycosides
Epinephrine
Insulin
Levodopa
Lidocaine
Monoamine oxidase inhibitors
Oral diabetes drugs such as glyburide
Prazosin
Quinidine
Rifampin
Theophylline

4.1.8 Contraindications and Side Effects:

The adverse effects of propranolol are generally mild and temporary. These side effects usually occur at the onset of therapy and diminish over time. Propranolol is contraindicated in patients with sinus bradycardia, cardiogenic

shock, bronchial asthma, or allergic to propranolol. Use with care in patients with congestive heart failure.

Side Effects: Sinus bradycardia, hypotension, AV block, congestive heart failure in patients with preexisting left ventricular dysfunction, depression, confusion, hallucinations; or Mask signs of hypoglycemia, Agranulocytosis, decreased sex drive, impotence, or difficulty having an orgasm; nausea, vomiting, diarrhea, constipation, stomach cramps; sleep problems (insomnia); or tired feeling.

Please refer to Appendix O & P - Common Side Effects of Beta Blockers.

4.1.9 Supplier:

Propranolol will be provided free of charge to the patients and distributed by the Mays [name] Anderson Cancer Center, and the LBJ Pharmacy. Patients will receive monthly supplies.

4.1.10 Pill Calendar Diary (Appendix M, N):

A pill calendar diary will be submitted at each visit along with the pill bottle for verification. Calendars, empty bottles and any unused medication will be collected at each appointment before the next refill is given to the patient.

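### Footnote 8 of 8.1 gives self-monitoring patients no call trigger for a heart rate below 50 bpm, although 7.2 names that range for propranolol dose reduction

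*Combined protocol and SAP*

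**What the plan says.** The call rule is in footnote 8 under the table in section 8.1. Blood pressure and heart rate are checked in the clinic before the first dose. Blood pressure is checked again at 48 to 72 hours, in the clinic or by contact with research staff. After that, the "patient should continue to monitor blood pressure daily with their personal blood pressure machine, at their local pharmacy, or in the clinic". The rule then reads "If personally monitoring their blood pressure, the patient should contact the research nurse if the SBP is less than 110", followed by the two remaining triggers: "the DBP is less than 50 or heart rate 50-60 and showing symptoms at two different timepoints 24 hours apart".

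The dose rule for bradycardia is in section 7.2: "If the heart rate is less than 50 or 50-60 and showing symptoms at two different timepoints 24 hours apart", the dose goes down one level in Table E. It goes down a second level if bradycardia persists, and the drug is stopped if it persists again.

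The opening paragraph of section 7.0 has a broader, permissive rule. The dose can be reduced if the "heart rate is less than 60 or systolic BP is less than 110 or diastolic less than 50 and showing symptoms" on two occasions a day apart. It adds: "All dose reductions will be made in the clinic".

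Two other sections fix the meaning of 50 bpm. Section 5.1 titrates toward a heart rate of 50 to 80. Section 3.2.2 lists bradycardia under 50 among the contraindications that exclude a patient.

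**The concern.** Footnote 8 carries the second half of the heart-rate condition in 7.2 and drops the first. The range that the rest of the protocol treats as too slow is therefore the one for which the footnote gives no instruction to call.

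What is at stake is patient safety between visits. Slow pulse heads the list in section 4.1.8: "Side Effects: Sinus bradycardia, hypotension, AV block". Daily readings may be taken away from the clinic, while dose reductions happen only in it, so 7.2 can act on a home reading only if that reading reaches staff. The exposure also rises during the study. In patients aged 65 or under who tolerate the starting dose, "the dose will be increased to 40 mg by mouth twice a day at the start of the second month of therapy", that is, from 2 × 20 = 40 mg a day to 2 × 40 = 80 mg a day.

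**Working it through.** No sample size, error rate or interval is involved. The check sets the heart-rate rules side by side.

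**Inputs.** Footnote 8 of 8.1 (when the patient calls), 7.2 (when the dose is reduced), 7.0 (when it may be reduced), 5.1 (target range), 3.2.2 (contraindication).

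**Step 1: how 7.2 can be read.** The sentence has no comma. Under reading A the symptom condition applies only to 50-60, so any rate below 50 triggers a reduction. Under reading B it applies to both bands, so a rate below 50 triggers a reduction only with symptoms on two occasions a day apart. Sections 5.1 and 3.2.2 lean toward A: a rate of 50-60 lies inside the target, so asking for symptoms there makes sense, whereas below 50 is outside the target and is a contraindication with no mention of symptoms. That is an inference, so both readings are kept.

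**Step 2: compare state by state.** In the table, symptoms means symptoms on two occasions a day apart.

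| Heart rate | Symptoms | 7.2, reading A | 7.2, reading B | Footnote 8 heart-rate trigger |
|---|---|---|---|---|
| below 50 | no | reduce | no action | none |
| below 50 | yes | reduce | reduce | none |
| 50-60 | no | no action | no action | none |
| 50-60 | yes | reduce | reduce | call |

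The second row is a mismatch under both readings, and the first under reading A only. Every mismatch is below 50 bpm. The table shows where the two rules part. It says nothing about how often a patient would be in either row.

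**Step 3: could another trigger cover the gap?** The two blood pressure triggers in footnote 8 would prompt a call only if systolic pressure were also under 110 or diastolic under 50. Section 7.0 includes rates below 50, because they are below 60, but it governs what the clinic may do and not when the patient calls. No other section supplied tells a patient to call for a rate below 50.

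**Step 4: test the correction.** Suppose both footnote 8 and 7.2 read: below 50, comma, or 50-60 with symptoms. Then the four rows give reduce and call, reduce and call, neither, reduce and call. The two rules agree in every row. If the comma went into footnote 8 alone and 7.2 were meant as reading B, the first row would prompt a call with no directed reduction. That is why 7.2 needs the same punctuation.

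**The case against.** The strongest reply is that this is an evident slip with limited consequence. The rules addressed to clinicians treat a rate below 50 as out of range, and nothing suggests that the sponsor meant to exempt it. A sensible patient or nurse would probably act on 45 bpm if 55 bpm already calls for contact. Section 7.0 also allows a reduction for side effects with no heart-rate threshold, section 6.1 requires adverse events to be assessed at each visit, daily readings may be taken in the clinic, and monthly drug supply and diary collection bring some further contact.

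Most of that stands as context. It supports calling this a drafting omission, and it limits the likely harm. It does not put the missing trigger into the call rule, which should not leave the patient to infer its most serious case.

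Three stronger readings are tempting, and the documents do not support them.

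- A reader might infer that patients are never told to call for a very slow pulse. What they hold in their hands is in the pill diaries (Appendices M and N) and the side-effect sheets (Appendices O and P), whose text is not shown. An instruction there cannot be ruled out.
- A reader might infer that the threshold in 7.0 is also wrong. It already takes in rates below 50, and it permits a reduction where 7.2 directs one. No error in it has been shown.
- A reader might infer that every patient's dose doubles in month two. The increase requires that the starting dose was tolerated without hypotension or bradycardia, and patients over 65 stay at 20 mg twice a day.

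**Conclusion.** The inconsistency is real and holds on either reading of 7.2: footnote 8 omits a heart rate below 50 bpm from the patient's call rule. It should be corrected as an internal inconsistency in a safety rule, most likely a drafting omission and not a deliberate threshold.

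Its size is one of the two heart-rate bands named in 7.2, the lower one. The documents give no expected rate of pulses below 50, so how many of the 20 planned patients could be affected is not estimated. A reader might infer some effect on the feasibility criteria in section 12.0 or on the toxicity criterion there, but nothing in the documents allows one to be shown, and none is claimed.

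The conclusion rests on two conditions. First, the footnote is taken as written, with no fuller instruction in the handouts. Second, the patient has a pulse reading at all: the daily-monitoring sentence names only blood pressure, and heart rate enters through the call rule.

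**What to change.** In footnote 8, insert *less than 50, or* immediately before the 50-60 band and leave the symptom condition attached to 50-60. Put the same comma into the heart-rate condition of 7.2. The call rule and the dose-reduction rule then match, and any rate below 50 counts whether or not there are symptoms. Check Appendices M to P, in English and Spanish, against the corrected footnote, and change them only if they differ. Leave 7.0 and the escalation rules in 4.1.4, 5.1 and 5.3 as they are.

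The cost is a wording amendment, plus a few more patient calls and possibly some extra clinic visits, since reductions are made there. No patients or data collection are added, and no statistical figure changes.
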